7.1.2.5 Tumor Imaging and Assessment of Disease

Tumor imaging consists of standard of care imaging at baseline during the screening period, including FDG-PET/CT with contrast-enhanced computed tomography (CT) of the chest, abdomen, and pelvis.

For measurement of response, 2014 criteria as described in “Recommendations for Initial Evaluation, Staging, and Response Assessment of Hodgkin and Non-Hodgkin Lymphoma: The Lugano Classification” will be used (see Appendix 14.3).²³

- **Baseline imaging** must be performed prior to initiating study drug therapy as outlined in the study calendar including PET/CT and diagnostic quality CT. Additional baseline imaging may be performed as indicated for standard of care and clinical purposes including MRI, or CT imaging of the neck.
- **Interim imaging** should be performed prior to Cycle 5, 9, and 12 as outlined in sections 6.1 and 6.2. Imaging prior to cycle 9 should be a PET/CT with concurrent diagnostic CT, while other interim imaging assessments can be a diagnostic CT alone unless additional imaging is clinically necessary.
- **Off study:** For patients only completing part A, the post cycle 8 scan will serve as the off study imaging. For patients participating in part B, end of treatment tumor imaging performed should be performed after cycle 14 day 1 and as close to the end of study visit (4-6 weeks, +/-7 days after cycle 14 day 1) as possible. Imaging should include PET/CT with diagnostic quality CT.

All CT scans should be performed with IV contrast unless contraindicated, and abdominal and pelvis scans should be performed with oral contrast.

All CT and FDG-PET/CT scans are to be interpreted locally; central review of radiology will not be performed. For response assessments with a PET/CT, the clinical read and images will be reviewed by the investigator, and if there are disagreements, a third person (radiologist) will adjudicate.

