Shown in the table below are the lower one-sided 80% and 90% confidence limits for a variety of observed response rates among 42 patients.

Observed response proportion	Point estimate	Lower one-sided 80%, 90% confidence limit
27/42	64%	57%, 53%
31/42	74%	66%, 63%
36/42	86%	79%, 76%
38/42	90%	85%, 82%

We also propose interim efficacy evaluations with suspension rules. Primary progressive disease with rituximab monotherapy²⁶ and rituximab + chemotherapy¹ is rare, with most cases likely due to occult transformation. If 2 out of the first 20 (or fewer) subjects have primary progressive disease (an observed rate of 10% or higher), the study will be suspended to enrollment pending the recommendations of an ad-hoc safety committee. The lower one-sided 80% confidence limit for 2/20 is 4%, and therefore with such an occurrence (or among fewer than 20 patients) we'd be reasonably confident that the true rate is greater than 4%. Since progressive disease in this population has been rare, this rule is relatively strict. Patients who

have suspected or biopsy-proven transformed disease will not count as an event for the purposes of this analysis. Since pseudo-progression can be seen with immunotherapy drugs like mosunetuzumab, subjects with overall reduced tumor burden that meet criteria for progression due to discordant response among tumor sites will also not count as an event for the purposes of this analysis.

We also acknowledge that chemo-immunotherapy is associated with high overall response rates of around 90%¹, and we propose an interim analysis with a suspension rule for lack of sufficient efficacy. If 14 or fewer of the first 20 subjects do not achieve an objective response of PR or CR as best response by the end of study treatment (an observed rate of 70% or less), the study will be suspended to enrollment pending the recommendations of an ad-hoc safety committee. The upper one-sided 80% confidence limit for 14/20 is 79%, and therefore with such an occurrence we'd be reasonably confident that the true response rate is less than 80%, the loose benchmark that we are using to define success for this trial.

In both cases, the ad-hoc safety committee may recommend changes to the protocol and its analysis based on updated information, closure of the protocol, or continued accrual with no modifications.

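### The 2-of-20 primary-progression rule lets undefined, unconfirmed suspicion of transformation remove events, so it is more lenient than the plan describes

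*Combined protocol and SAP*

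**What the plan says.** All the main elements are in the interim efficacy text of Section 8.0.

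- **Background.** Primary progressive disease on rituximab monotherapy or rituximab plus chemotherapy "is rare, with most cases likely due to occult transformation".
- **Trigger.** "If 2 out of the first 20 (or fewer) subjects have primary progressive disease (an observed rate of 10% or higher"), enrollment is suspended until an ad hoc committee has made recommendations.
- **Justification.** The plan gives a lower one-sided 80% limit of 4% for 2/20 and adds: "Since progressive disease in this population has been rare, this rule is relatively strict".
- **First exclusion.** Patients who "have suspected or biopsy-proven transformed disease will not count as an event for the purposes of this analysis".
- **Second exclusion.** Because of pseudo-progression, subjects with overall reduced tumor burden "that meet criteria for progression due to discordant response among tumor sites will also not count as an event".
- **Consequence.** The committee may recommend protocol changes, closure, or continued accrual without modification.

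Elsewhere, Section 5.3.2 makes the trial open-label and Section 7.1.2.5 has scans read locally: "central review of radiology will not be performed". Section 7.1.6.3 mentions tumor biopsy only as standard-of-care workup when remission status is equivocal. We found no definition of suspected transformation, no confirmation requirement for this rule, and no operating characteristics after the exclusions.

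**The concern.** The rarity that justifies the rule is the rarity of all primary progression, transformation included. The trial's count leaves transformation out. A threshold of 2 in 20 that looks demanding against the first quantity is less demanding when applied to the second.

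The weak point is the word *suspected*. Excluding biopsy-proven transformation rests on a verifiable fact. Excluding suspected transformation rests on an opinion formed once the progression is known. Since the plan's own premise is that most primary progressions are occult transformation, such a suspicion could plausibly be raised for many progressors. Whether the second event counts, and so whether enrollment pauses, may then turn on a judgement for which the plan sets no criteria.

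At stake is the earlier of the two efficacy suspension rules, in untreated patients who, under inclusion criterion 4, are forgoing approved therapies.

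**Working it through.** **Inputs from Section 8.0.** Trigger: 2 or more counted events in the first 20 subjects. Stated limit for 2/20: 4%. Share of progression due to transformation: described only as most cases, and only for rituximab-based treatment.

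**Assumptions (not in the documents).** *p* is the true all-cause primary-progression rate on this regimen. *f* is the share of progressions set aside as suspected or proven transformation. Discordant cases are ignored here.

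**1. The plan's own figure.** The exact (Clopper-Pearson) lower one-sided 80% limit for 2/20 is the 0.20 quantile of Beta(2, 19), which is 0.0414. This reproduces the stated 4%.

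**2. What that limit describes.** It bounds the rate of events that count, not of all progressions. Taking *f* as known, the matching all-cause limit is 0.0414/(1 − *f*): about 8.3% if half are set aside (0.0414/0.5) and 16.6% if three quarters are (0.0414/0.25).

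**3. Probability that the rule fires.** Counted events only accumulate, so reaching 2 at any point up to 20 subjects is the same as having 2 or more of 20. With *q* = *p*(1 − *f*):

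P = 1 − (1 − *q*)^20 − 20*q*(1 − *q*)^19

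For *p* = 10%:
- *f* = 0, *q* = 0.10: 1 − 0.122 − 0.270 = 0.608
- *f* = 0.50, *q* = 0.05: 1 − 0.358 − 0.377 = 0.264 (unrounded terms)
- *f* = 0.75, *q* = 0.025: 1 − 0.603 − 0.309 = 0.088

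| All-cause rate *p* | *f* = 0 | *f* = 0.50 | *f* = 0.75 |
|---|---|---|---|
| 4% | 0.190 | 0.060 | 0.017 |
| 10% | 0.608 | 0.264 | 0.088 |
| 20% | 0.931 | 0.608 | 0.264 |

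**4. The opposite case.** If the regimen's failures are untransformed and recognised as such, they all count. The rule then fires with probability 0.608, 0.824 and 0.931 at untransformed rates of 10%, 15% and 20%.

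**5. What counting unproven cases would recover.** The *f* = 0 column is an upper bound, because biopsy-proven cases would remain excluded. Two illustrations at *p* = 10% with three quarters now set aside (0.088):
- If a quarter of all progressions are biopsy-proven and half only suspected, counting the latter gives *q* = 0.075 and P = 0.449.
- If half are proven and a quarter only suspected, *q* = 0.05 and P = 0.264.

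If nearly all suspected cases are confirmed, the gain is small.

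**6. False alarms.** With every progression counted, P is 0.060 at a true 2% rate and 0.190 at 4%. These are ceilings for the proposed change.

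**The case against.** A reader might infer that the rule could rarely fire, or that most of its ability to detect an excess is gone. The documents do not support that. The statement about most cases is hedged, and it describes rare progression on rituximab-based treatment, not on this regimen. Holding *f* at 50% or 75% while *p* rises assumes that the regimen's own failures are also mostly called transformation. If excess failure is untransformed and recognised as such, step 4 applies. As an assumed mixture, take a 4% background of which three quarters is excluded (1% countable), plus 10% genuine failure. That leaves 11% countable and a firing probability of about 0.66. This objection stands, and the size of the loss is conditional.

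Excluding transformation is also a reasonable design choice. Eligible histologies are follicular lymphoma grade 1-2 or 3a and marginal zone lymphoma, and occult transformation is arguably a different disease already present at entry. That supports excluding proven cases. It does not support an undefined, unconfirmed category.

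Finally, set-aside patients are not invisible. The companion response-rate rule has no transformation exclusion, any on-treatment death suspends accrual, and the institutional committee reviews the trial at least annually. The response-rate rule is a weak backstop, however. Read by its parenthesis (70% or less responding), it needs 6 or more non-responders in 20. If progressors were the only non-responders (an assumption; stable disease would raise these figures), the probability is about 0.01 at 10% progression and 0.20 at 20%. It also uses best response by the end of treatment, up to 14 cycles of 21 days, whereas progression can be seen on the CT before cycle 5. Its main clause conflicts with its parenthesis and needs separate correction.

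Nor do the documents say that the treating investigator alone decides what is suspected: they name no one. Section 7.1.2.5 sends PET/CT disagreements to a third reader, but that settles the scan reading, not transformation.

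**Conclusion.** The point holds in limited form. The rule is set against a rare all-cause background but counts only what is left after an exclusion that includes unverified suspicion. It is therefore more lenient than its description suggests and open to judgement after the event. At 10% all-cause progression, the chance of a pause falls from an upper bound of 0.61 to 0.26 or 0.09 if half or three quarters of progressions are set aside. It does not fall if the failures are untransformed and recognised as such. The progression rates and set-aside shares are assumptions, and how suspected cases divide into proven and unproven is unknown. The calculation therefore shows how far the rule could weaken, not how far it will. The defect does not depend on those assumptions: an undefined term decides whether an event counts. It should be corrected, since the change is small and the rule only pauses enrollment for review.

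**What to change.** Amend the transformation sentence in Section 8.0 so that only biopsy-proven transformation is excluded. Suspected but unproven transformation counts toward the 2/20 trigger, and the suspicion goes to the ad hoc committee as context. The judgement is kept but moves to after the trigger, to a body that may already recommend continuing unchanged.

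Keep the separate exclusion for discordant progression with overall reduced tumor burden; it has its own rationale and is not at issue here. Mandate no biopsy. It would also help to report the rule's operating characteristics after exclusions, over a stated range of set-aside shares.

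The cost is one changed sentence and occasional extra pauses for committee review, with probability at most 0.06 at a true progression rate of 2% and 0.19 at 4%.

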Objectives include gaining a preliminary assessment of the potential efficacy of this regimen. This will be defined as the percentage of patients that achieve a complete remission (CR) following study treatment as the primary end point, best ORR as a secondary end point. Exploratory endpoints include with PFS and OS. A simple binary proportion will be used to estimate CR and ORR, and the Kaplan-Meier method will be used to estimate PFS and OS.

Combination chemotherapy with a CD20 monoclonal antibody is highly efficacious in the treatment of indolent lymphomas, but short and long term toxicities can be seen¹⁻³. Since these studies did not all use PET-based assessments, it can be challenging to determine a reasonable

benchmark. However, recent retrospective studies would suggest the CR rate to upfront treatment is around 80%²⁵. Given potential for less toxicity with the proposed treatment, an observed CR rate that is at least as high as this benchmark would be considered promising, pending examination of other endpoints plus toxicity data. Therefore we would consider this study to be successful and merit further investigation if the observed best response as CR rate that is at least 80% among the patients treated. We propose to treat a total of 42 patients, this number not based on considerations of statistical power to reject a null hypothesis, rather on considerations of feasibility and ability to accrue. We anticipate enrolling roughly 42 patients over a 30-month period, but if the protocol is open for 36 months before 42 patients have been enrolled, consideration will be given to closing the study. If we enroll 42 patients, 34 or more complete responses would meet this benchmark. Shown in the table below is the probability of 34 or more responses among 42 patients for a variety of assumed-true CR rates. A subject will be defined as efficacy evaluable if they have had at least one response assessment. Subjects who come off study treatment for any reason prior to a response assessment will not be considered response evaluable and will not be replaced. If fewer than 42 subjects are evaluable for response after completion of the study, we will recalculate the below tables with a goal of achieving a CR as best response in at least 80% of patients.

Assumed-true CR rate	Probability of 34 or more responses among 42 patients
.65	.02
.70	.08
.75	.24
.80	.53
.85	.83
.90	.98

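### The response-rate suspension rule in SAP section 8.0 is worded in reverse: as written it is triggered by 6 or more responders among the first 20, not by 14 or fewer

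*Combined protocol and SAP*

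**What the plan says.** The rule is in section 8.0, after the tables for 42 patients. The plan notes that "chemo-immunotherapy is associated with high overall response rates of around 90"% and proposes "an interim analysis with a suspension rule for lack of sufficient efficacy". The trigger, judged once treatment is complete, is worded "If 14 or fewer of the first 20 subjects do not achieve an objective response of PR or CR as best response". The parenthesis and consequence follow: "an observed rate of 70% or less), the study will be suspended to enrollment pending the recommendations of an ad-hoc safety committee".

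The next sentence justifies the cut-off: "The upper one-sided 80% confidence limit for 14/20 is 79"%, so that with such a result one would be "reasonably confident that the true response rate is less than 80"%, which the plan calls its loose benchmark for success.

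Three other parts of the plan bear on this:

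- Section 8.0 also has a primary-progression rule, under which two events in the first 20 or fewer subjects suspend enrollment. For both rules the committee may recommend changes, closure, or unchanged continuation.
- Section 5.9 allows termination by decision of the principal investigator and an ad hoc committee once a stopping rule is met. Section 10.0 says the review committees evaluate stopping rules.
- The response-rate rule is not restated anywhere else, so no correct version overrides this sentence.

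**The concern.** The trigger counts subjects who fail to respond and suspends when that count is low. A low count of failures is a good result. The sentence therefore does the reverse of what the paragraph says it is for.

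This is the only interim rule based on the response rate. Committees asked to evaluate stopping rules will work from the written trigger. If they follow the text, a regimen performing at the plan's own 90% reference is paused almost surely, and one with a very low response rate usually continues. If they follow the evident intent, they depart from the written rule after seeing data. Neither is a good position for a pre-specified rule.

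**Working it through.** **Inputs (all section 8.0).** n = 20 subjects; cut-off 14; reference ORR about 90%; stated upper one-sided 80% limit for 14/20 of 79%.

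**Step 1: reproduce the plan's figure, with 14 as responders.**
- Wald: 0.70 + 0.8416 × √(0.70 × 0.30 / 20) = 0.786
- Wilson: 0.778
- Exact (Clopper-Pearson): 0.799

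The stated 79% matches the Wald limit after rounding and is within one point of the exact limit. The figure is sound for 14 *responders*.

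**Step 2: try it with 14 as non-responders.** Responders are then 20 − 14 = 6, a rate of 6/20 = 30%. The upper one-sided 80% limit is 0.386 (Wald) or 0.418 (exact). Neither is near 79%. The justification fits only a trigger of 14 or fewer responders.

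**Step 3: operating characteristics.** Let X be the number of responders, binomial (20, p), where p is the true ORR.
- As written: P(suspend) = P(20 − X ≤ 14) = P(X ≥ 6)
- As intended: P(suspend) = P(X ≤ 14)

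| True ORR | As written | As intended |
|---|---|---|
| 90% | >0.999 | 0.011 |
| 85% | >0.999 | 0.067 |
| 80% | >0.999 | 0.196 |
| 70% | >0.999 | 0.584 |
| 60% | 0.998 | 0.874 |
| 50% | 0.979 | 0.979 |
| 40% | 0.874 | 0.998 |
| 30% | 0.584 | >0.999 |
| 20% | 0.196 | >0.999 |
| 10% | 0.011 | >0.999 |

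The columns are mirror images: the written rule at p behaves as the intended rule at 1 − p, and they meet at 50%.

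**Step 4: timing, for the optional clarification only.** Section 8.0 says "We anticipate enrolling roughly 42 patients over a 30-month period", which is 42/30 = 1.4 per month if accrual is uniform (an assumption).
- Subject 20 enters at 20/1.4 = 14.3 months.
- If that subject completes Part B, cycle 14 day 1 is 13 × 21 = 273 days after cycle 1 day 1. The end-of-treatment scan is aimed at the visit 4 to 6 weeks later (section 7.1.2.5, ignoring its ±7-day window), so day 301 to 315, or 9.9 to 10.3 months.
- The result is then known at about month 24.2 to 24.6, when 1.4 × 24.2 = 33.9 to 1.4 × 24.6 = 34.4, about 34 of 42, are enrolled.
- If subject 20 stops after Part A, at about day 8 × 21 = 168 (5.5 months), enrollment is 1.4 × (14.3 + 5.5) = 27.7, about 28.
- If accrual takes the 36 months that section 8.0 contemplates (42/36 = 1.17 per month), about 32 are enrolled even after full Part B.

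**The case against.** The strongest reply is that no competent reader would apply the sentence literally. The paragraph names lack of efficacy as the purpose and reads 14/20 as a response proportion, so the intent is plain and the numerical design is sound. That stands, and it makes this a drafting error rather than a flawed design. It does not make the operative sentence right.

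Some stronger readings are tempting, and the documents do not support them:

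- *A reader might infer that the parenthesis settles the direction.* It does not. The 70% is not labelled as a response or a non-response rate. The purpose and the confidence-limit sentence settle it.
- *A reader might infer that the trial has no other interim protection against inefficacy.* The primary-progression rule is a second one. If countable progression occurred in 10% or 20% of subjects (assumed rates), P(2 or more of 20) would be 0.61 or 0.93. It is only a partial backstop, because stable disease never triggers it.
- *A reader might infer that any weak regimen would keep enrolling.* That holds only at very low response rates. The literal rule also suspends with probability 0.87 at ORR 40% and 0.98 at 50%.
- *A reader might infer that a false trigger closes the study.* It causes a pause and a review; the committee may let accrual continue unchanged.
- *A reader might infer that the rule can spare no more than about 8 of 42 patients.* That is not an upper bound. It needs uniform accrual, a 20th subject who completes Part B, and a wait for all 20. Best response may be settled earlier, for example by PR on the cycle 4 CT, and nothing in section 8.0 requires waiting once the outcome is determined.

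**Conclusion.** The rule is wrong as written and must be corrected. At the plan's 90% reference ORR, the literal trigger suspends with probability above 0.999, against 0.011 for the rule the paragraph justifies. At 10% ORR, it suspends with probability only 0.011, against above 0.999. These figures assume independent subjects, a common true ORR and all 20 counted, and rest on no outside data.

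The error lies in the direction of one sentence. The cut-off of 14, the sample of 20 and the confidence-limit argument are unaffected. Timing is a secondary matter of clarity, not an error: the count enrolled when the rule reads out runs from about 28 to about 34 of 42 under the assumptions shown.

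**What to change.** **Required.** Remove the negation and label the rate. For example: *Enrollment is suspended, pending the ad-hoc committee's recommendations, if no more than 14 of the first 20 subjects have PR or CR as their best response over study treatment, that is, a response rate of 70% or lower.* The confidence-limit sentence can stay as it is. The cost is one sentence in section 8.0, with no extra patients or procedures and no change to the threshold.

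**Optional.** State that the rule is met as soon as a sixth response-evaluable subject among the first 20 ends study treatment without PR or CR. If all 20 are evaluable, this is the same threshold (20 − 14 = 6) and leaves P(suspend) unchanged, but it can act sooner. The words *response-evaluable* matter: section 8.0 says subjects who leave treatment before any response assessment are not evaluable, and a running count without that limit would count them as failures. The plan should also say how the cut-off applies if fewer than 20 of the first 20 are evaluable. This costs one further clause.

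### The interim lack-of-efficacy rule counts overall response but is justified against the CR success benchmark, and no interim rule counts CR

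*Combined protocol and SAP*

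**What the plan says.** All of this is in Section 8.0.

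- **Source of the 80%.** It is a CR figure: "recent retrospective studies would suggest the CR rate to upfront treatment is around 80" percent.
- **Success.** The study merits further investigation given "the observed best response as CR rate that is at least 80% among the patients treated". In counts: "If we enroll 42 patients, 34 or more complete responses would meet this benchmark".
- **Sample size.** 42 was set by feasibility, "this number not based on considerations of statistical power to reject a null hypothesis".
- **Lack-of-efficacy rule.** The paragraph opens by noting that chemo-immunotherapy gives "high overall response rates of around 90" percent. The rule then counts "objective response of PR or CR as best response by the end of study treatment (an observed rate of 70% or less"). The upper one-sided 80% limit for 14/20 is given as 79%, from which the plan concludes that "the true response rate is less than 80%, the loose benchmark that we are using to define success for this trial".
- **Consequence.** Enrollment is suspended until an ad-hoc committee advises. The committee may recommend continuing unchanged.
- **Other interim efficacy rule.** It counts primary progression (2 of the first 20 or fewer). Neither rule counts CR.

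**The concern.** The interim endpoint and the benchmark belong to different quantities. The 80% that defines success is a CR rate, while the count compared with it includes partial responses. The overall response reference in the same paragraph is about 90%.

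The gap matters because the two rates can lie far apart. Section 4.3 reports 63% ORR and 43% CR for mosunetuzumab in relapsed or refractory disease. A regimen that produces many PRs and too few CRs can clear the interim look while its success criterion is slipping out of reach. At the extreme, 20 PRs and no CRs would pass. Enrolled subjects are previously untreated, and Section 5.1 requires documented understanding that they are forgoing approved therapies. The committee should therefore hear when the plan's own benchmark is lost.

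**Working it through.** **Inputs from the documents.** Success is at least 34/42 CR. The interim cutoff is 14/20. Reference ORR is 90%. Accrual is 42 patients over 30 months (Section 8.0). There are up to 14 cycles of 21 days (Section 5.3), with final imaging near a visit 4–6 weeks after cycle 14 day 1 (Section 7.1.2.5).

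**Assumptions.** True CR rates of 50%, 60% and 65% are illustrative; the SAP's own table starts at 65%. Subjects are independent and accrual is uniform.

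**Reading of the rule.** The sentence literally says "If 14 or fewer of the first 20 subjects do not achieve an objective response", which would suspend a trial with 6 or more responders. The 70% in parentheses and the 14/20 limit show that 14 or fewer *responders* is meant. That reading is used here.

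**1. Reproduce the plan's figures.** Upper one-sided 80% limit for 14/20:
- Wald: 0.70 + 0.8416 × √(0.70 × 0.30/20) = 0.786.
- Exact (Clopper-Pearson): 0.799.

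The stated 79% is consistent with these. P(X ≥ 34), X ~ Bin(42, p), gives .019, .080, .243, .531, .831 and .979 for p = .65 to .90, matching all six table entries.

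**2. Behaviour of the ORR rule.** P(suspend) = P(X ≤ 14), X ~ Bin(20, ORR). This is 19.6% at ORR 80%, 6.7% at 85% and 1.1% at 90%. The CR rate does not enter.

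**3. Chance of meeting the CR criterion, and of passing when it is already lost.** With 11 or fewer CRs in 20, the most attainable is 11 + 22 = 33 of 42. The last two columns are exact trinomial (CR / PR / no response).

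| True CR | P(≥34/42) | P(≤11/20 CR) | P(pass and ≤11 CR), ORR 90% | Same, ORR 80% |
|---|---|---|---|---|
| 50% | 0.003% | 74.8% | 73.7% | 56.0% |
| 60% | 0.3% | 40.4% | 39.4% | 24.7% |
| 65% | 1.9% | 23.8% | 22.8% | 11.3% |

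**4. When the benchmark is out of reach.** With 9 evaluable non-CRs, the best attainable rate is (N − 9)/N. This rises with N and equals 33/42 = 78.6% at N = 42, so it is below 80% for every evaluable N up to 42. The count must be of *evaluable* subjects. Section 8.0 drops those who leave before any response assessment and resets the goal to 80% of the rest. If one of nine treated non-CRs was never assessed, 33/41 = 80.5% still succeeds; if two were not, 33/40 = 82.5% does.

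**5. Cost of a 9-non-CR referral at true CR 80%.**
- Within the first 20: P(≤11/20) = 1.0%.
- Over all 42: 1 − .531 = 46.9%, in every case with the benchmark already missed.

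**6. Patients it could spare.** Cycle 14 day 1 falls 13 × 21 = 273 days after the start, and 28–42 days more gives 301–315 days, about 10 months. Accrual is 42/30 = 1.4 per month, so about 14 more patients enrol during the lag. If the ninth non-CR is the k-th patient enrolled, about max(0, 28 − k) are spared. Here P(k) = C(k−1, 8)(1−p)⁹p^(k−9), where p is the CR rate. The mean is about 10 at CR 50%, 6 at 60% and 4 at 65%.

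**The case against.** The strongest reply is that the rule is sound as written. CR is a subset of overall response, so an ORR below 80% implies a CR rate below 80%. A reader might infer that comparing an ORR limit with a CR benchmark is a statistical error. It is not, and that part of the reply stands in full. What remains is that the rule works in one direction only, and the text does not say so.

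Second, this is a pilot without a power calculation, and its objective is to estimate. The SAP tabulates limits for 27/42 and 31/42, both below the benchmark. A reader might infer that the primary question is settled once 34/42 is unreachable. The documents do not support that: estimation continues, and 80% marks a promising result subject to other endpoints and toxicity. This stands, and it is why any CR trigger should be a referral and not a stop.

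Third, a reader might infer that a CR look at 20 would save the remaining 22 patients. No accrual pause is planned. Patient 20 enrols at about 20/1.4 = 14.3 months and is finally assessed about 10 months later, when about 34 are enrolled and about 8 remain. The existing ORR rule has the same lag.

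Fourth, within the SAP's own tabulated range an early trigger is infrequent: P(≤11/20) is 24%, 11% and 4% at CR 65%, 70% and 75%. That is fair and limits the gain.

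Other protections exist (the progression rule, at least annual monitoring committee review, Part B for subjects not in CR), but none compares the CR count with the benchmark.

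**Conclusion.** The point holds as a cheap improvement to the plan. The lack-of-efficacy rule is a valid necessary-condition screen, but it is insensitive to the primary endpoint, and CR has no interim check. A regimen far below the CR target *can* pass, and at 90% ORR nearly always does (98.9%); at 80% ORR it passes about 80% of the time. No error-rate guarantee is broken, because the plan sets none.

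The size rests on assumed CR rates, binomial independence and the evident meaning of the 14/20 sentence. The patients-spared figures also assume uniform accrual, about 10 months to final assessment for every non-CR, and closure on referral. They would change if non-CR subjects left treatment earlier or if the committee let accrual continue.

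**What to change.** Amend Section 8.0 as follows:

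1. Keep the ORR rule. State that 80% is the CR benchmark, that the rule only screens for a necessary condition of reaching it, and that passing says nothing about CR. In the same edit, correct the sentence so that it refers to 14 or fewer responders.
2. Add a non-binding referral to the ad-hoc committee once 9 response-evaluable subjects have completed or left study treatment without a CR as best response. State that the committee may continue accrual for estimation.
3. Say which denominator governs success, since the section refers both to patients treated and to evaluable subjects.

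Do not simply replace the 80% reference with 90%. By the plan's own logic (upper one-sided 80% limit below the reference), 90% would support a cutoff of 16/20 (exact limit 88%) and leave 14/20 unexplained.

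The cost is SAP wording and a running tally of CR data already collected. At a true CR rate of 80%, referral occurs with about 1% probability within the first 20 and about 47% over all 42, always after the benchmark is missed. If the CR referral is not wanted, the minimum is item 1 plus a plain statement that the primary endpoint has no interim futility check.
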